8.1.2.1 Severity of Chronic Cough Diary (SCCD)

Study participants' assessment of frequency, severity of cough, disruption due to cough and disruptions of sleep will be recorded electronically every day from screening until the end of the intervention period using the SCCD.

The SCCD is a novel 14-item PRO questionnaire, asking the participant to assess experiences with their cough during the past 24 hours. Study participants will rate the frequency (items 1-4), severity (items 5-8), disruptions due to cough (items 9-11 and 14) and disruptions of sleep (items 12-13) using verbal rating scales (VRS) and are asked to enter their daily assessments directly into the handheld device at home. The completion of the SCCD takes approximately 5 minutes.

The daily recording of the SCCD will start at Visit 1 and will be continued daily until the SFU visit or at early termination for those study participants discontinuing the study before completion.

SCCD scores will be calculated based on study participants' responses to single items.

The SCCD is a PRO, which has been newly developed by Bayer. The SCCD underwent cognitive interviews (CIs) confirming the content validity, the ease of comprehension, interpretation and completion prior to initiation of this study. Psychometric and other measurement properties of the SCCD are planned to be assessed using data from this trial. Results from the CIs and the psychometric analyses are aimed to confirm the appropriateness of the instrument for use in clinical Phase 3 in potential support of label claims.

Training and instructions will be provided to participants in terms of how to complete the questionnaire.

8.1.2.2 Cough Severity Visual Analog Scale

Study participant assessment of cough severity will be recorded electronically daily using the Cough Severity Visual Analogue Scale (VAS).

The Cough Severity VAS is a single item instrument, asking the study participant to assess the severity of his/her cough using a 0-100 VAS. This is a vertically oriented line ordered from 0-100, on which the study participants indicate the severity of their cough by crossing the line at the point that that best reflected the perception of the severity of their cough on

their handheld device. The completion of the Cough Severity VAS will take less than 1 minute.

The daily recording of the Cough Severity VAS will start at Visit 1 and will be continued daily until the SFU visit or at early termination for those study participants discontinuing the study before completion.

The Cough Severity VAS response option is known for its simplicity and practicality and is commonly used in clinical research for the measurement of a variety of clinical phenomena (20), including for the assessment of cough (16). The scale response range is from ("No Cough") to 100 ("Extremely Severe Cough"). A change of 17 scale units on a VAS has been reported to be perceived as important to subjects with acute cough (21). Clinical trial endpoints evaluating treatments for chronic cough include an endpoint of '≥ 30 scale units Reduction From Baseline in Cough Severity Visual Analog Scale (VAS) Score'(22).

In this trial, the Cough Severity VAS will assess key secondary and other efficacy endpoints. Scores from the Cough Severity VAS will also be used to investigate psychometric properties of the SCCD.

8.1.2.3 Patient Global Impression of Severity (PGI-S) and Patient Global Impression of Change (PGI-C)

PGI-S and PGI-C will be assessed on the tablet device at predefined visits according to the SoA or at earlier termination for those study participants discontinuing the study before completion.

PGI-S

Study participants rate the severity of cough using the PGI-S scale experienced at the time point of the assessment (no recall period).

The PGI-S is a single item instrument. Study participants respond to the PGI-S using a 5-point verbal rating scale: a score of 0 = "No cough", 1 = "Very mild", 2 = "Mild", 3 = "Moderate", 4 = "Severe", 5 = "Very severe" and will enter their assessment on a tablet device during study visits. The PGI-S is being included in the trial as a reference measure for assessment of psychometric and other measurement properties of the newly developed SCCD.

PGI-C

Study participants rate the change in the severity of their cough using the PGI-C scale since starting study intervention at the different assessment time points respectively. Study participants respond using a 7-point verbal rating scale: a score of 0 = "Very much better", 1 = "Much better", 2 = "A little better", 3 = "No change", 4 = "A little worse", 5 = "Much worse" and 6 = "Very much worse". The PGI-C is being included in the trial as a reference measure for assessment of psychometric and other measurement properties of the newly developed SCCD.

8.1.2.4 Leicester Cough Questionnaire

Study participants assessment of health related quality of life will be recorded electronically using the Leicester Cough Questionnaire LCQ (23).

The LCQ is a 19-item instrument that asks about the impact of chronic cough on various aspects of participants' lives using a recall period of two weeks. The 8 items: 1, 2, 3, 9, 10,

11, 14, 15 build the physical domain. 7 items: 4, 5, 6, 12, 13, 16, 17 build the psychological domain. Further 4 items: 7, 8, 18 and 19 build the social domain.

Study participants respond to the items using a 7-point Likert scale from 1 (all of the time) to 7 (none of the time) and will enter their assessments on a tablet device during study visits according to the SoA or at earlier termination for those study participants discontinuing the study before completion. Completion of the LCQ takes approximately five minutes.

The LCQ total score is calculated as a mean score for each of the three domains ranging from 1 to 7, with the LCQ total score ranging from 3 to 21. A clinically significant improvement in cough-specific quality of life (QoL), is indicated by a ≥ 1.3 -point increase in the LCQ total score from baseline (24).

In this trial, the LCQ will assess key secondary and other efficacy endpoints. Scores from the LCQ will also be used to investigate psychometric properties of the SCCD. The LCQ version used in this trial is © 2001. S. Birring, UK.

8.1.2.5 EQ-5D-5L

The EQ-5D-5L will be filled in on the tablet device during study visits according to the SoA or at earlier termination for those study participants discontinuing the study before completion. Completion of the EQ-5D-5L takes approximately 3 minutes.

The EQ-5D-5L is a self-administered generic and widely used measure of health status with well-documented reliability, validity and responsiveness in the general population as well as in various diseases. Use of this instrument will enable a comparison of effects of RUCC on health-related quality of life with an age-matched normative sample. The instrument comprises 5 dimensions and an overall assessment of health status on a VAS. The 5 dimensions include: mobility, self-care, usual activities, pain and discomfort, and anxiety and depression where the scores 1 to 5 indicate: having no problems, having slight problems, having moderate problems, having severe problems and being unable to do/having extreme problems. In addition, patients are asked to self-rate their own health today on a vertical 0-100 unit VAS, with 0 corresponding to "the worst health you can imagine", and 100 corresponding to "the best health you can imagine".

Descriptive assessment will be done on the basis of the VAS and on dimension level assessment basis. The EQ-5D-5L version used in this trial is "EQ-5D-5L Tablet" © 2009 EuroQol Group EQ-5D™.

8.2 Safety Assessments

8.2.1 Physical Examinations

A comprehensive physical examination should be performed by the investigator at Visit 1 (screening), Visit 2 (Day 0) and Visit 6 (Day 84 ±2). Any abnormal findings are to be recorded and reported as an AE/SAE (see Section 8.3.1).

8.2.2 Vital Signs

Vital signs will be assessed at the site visits as specified in SoA table. This will include blood pressure (BP) and heart rate (HR) measurements. BP will be measured by using a standard sphygmomanometer with an appropriate size cuff in the sitting position after 5 minutes of rest, in a quiet setting. Blood pressure measurements can be repeated once during the screening visit if medically justified (e.g. in order to avoid suspected “white-coat hypertension”.)

8.2.3 Electrocardiograms

ECGs in supine position will be assessed locally as safety measures: standard electrocardiograms (12-lead ECG) according to Goldberger / Einthoven and Wilson will be recorded after resting for at least 5 minutes at Visit 1 (screening), Visit 6 (Day 84 ±2) and SFU visit, as outlined in the SoA. The following parameters will be recorded in the eCRF: VR, PR interval, QRS duration, QT interval (corrected QT calculated according to the formulas of both Bazett and Fridericia will be automatically calculated in Rave).

(1) Fridericia’s correction: $QTc = QT/RR^{0.33}$

(2) Bazett’s correction: $QTc = QT/RR^{0.5}$

All ECG printouts will be identified with the SID as well as the date and time of recording and will be attached to participant’s file.

ECG printouts must be reviewed and evaluated locally by the investigator or clinicians with experience in ECG interpretation on the day of recording for safety and quality.

An overall investigator assessment of ECG will be provided (categories: “normal”, “abnormal, not clinically significant” and “abnormal, clinically significant”). All ECG findings will be reported in the eCRF and any clinically relevant abnormality will be documented as an AE.

8.2.4 Spirometry (Lung Function Test)

Lung function testing (spirometry) will be conducted at Visit 1 (screening) in accordance with Guidelines from ATS/ERS Task Force (25), which is a standard method of the practice in pneumology. Available lung function testing results will be considered as baseline if they are not older than 3 months prior to screening.

Lung function measurements and predicted parameters calculated by the device include but are not limited to the following:

- Date
- Forced vital capacity (FVC) (L)
- Forced expiratory volume in one second (FEV1) (L)
- FEV1/FVC ratio (%)
- Forced expiratory flow (FEF) (L/sec)⁶
- Peak expiratory flow (PEF) (L/sec)
- Total lung capacity (TLC) (L)
- Vital Capacity (VC) (L)
- Inspiratory Capacity (IC) (L)
- Tidal volume (TV) (L)
- Residual volume (RV) (L)

All measured parameters that are listed above have to be transferred into the eCRF. The FEV1/FVC ratio is the ratio of the forced expiratory volume in the first one second to the forced vital capacity of the lungs. If not provided automatically by the available spirometer on site, the following formula or online tools should be applied for manual calculation (25):

FEV1/FVC ratio (FEV1%)

$$FEV1ratio = \frac{FEV1}{FVC} * 100$$

Quantitative reverse transcription polymerase chain reaction (qRT-PCR) for SARS-CoV-2 nucleic acid detection (oropharyngeal swabs) and immunoassay for qualitative detection of IgG antibodies against SARS-CoV-2 antigen (serum) are to be performed at specified visits at the site (see Section 1.3 for details).

Since there is no established clinical relevance linked to increased ATIII activity in medical literature, it is concluded that at this stage of development, the increase in ATIII activity can be considered as not clinically relevant. In addition, given the potential for unblinding participants receiving active treatment with BAY 1817080, the results of ATIII measures at the other visits will not be communicated to study teams nor investigators until after unblinding of the study.

In the event of implausible results, the laboratory may measure additional parameters to assess the quality of the sample (e.g., clotted or hemolyzed) and to verify the results. The results from such additional analyses may neither be included in the clinical database of this study nor evaluated further. If the results are relevant, the investigator will be informed to determine follow-up activities outside of this protocol.

8.3 Adverse Events and Serious Adverse Events

The definitions of an AE or SAE can be found in Section 10.3.

AE will be reported by the participant (or, when appropriate, healthcare professional not involved in the study).

The investigator and any qualified designees are responsible for detecting, documenting, and recording events that meet the definition of an AE or SAE. They remain responsible for following up SAEs, or AEs considered related to the study intervention or study procedures, or those that caused the participant to discontinue the study intervention.

8.3.1 Time Period and Frequency for Collecting AE and SAE Information

All AEs and SAEs will be collected from the signing of the informed consent form (ICF) until the follow-up visit at the time points specified in the SoA (Section 1.3).

A detailed history of symptoms and complications as a result of cough (type, onset, duration and time of resolution) will be recorded at screening via a series of questions reflected on an

individual eCRF page as part of the participant's medical history. Worsening of any of the conditions listed on the aforementioned eCRF page or their first occurrence after signing the informed consent will be recorded as AEs.

Additional details on smell and taste related AEs will be collected.

All SAEs will be recorded and reported to the sponsor or designee immediately and under no circumstances should this exceed 24 hours, as indicated in Section 10.3. The investigator will submit any updated SAE data to the sponsor within 24 hours of it being available.

Investigators are not obligated to actively seek AE or SAE after conclusion of the study participation. However, if the investigator learns of any SAE, including a death, at any time after a participant has been discharged from the study, and he/she considers the event to be reasonably related to the study intervention or study participation, the investigator must promptly notify the sponsor.

8.3.2 Method of Detecting AEs and SAEs

The method of recording, evaluating, and assessing causality of AE and SAE and the procedures for completing and transmitting SAE reports are provided in Section 10.3.

Care will be taken not to introduce bias when detecting AEs and/or SAEs. Open-ended and nonleading verbal questioning of the participant is the preferred method to inquire about AE occurrences.

8.3.3 Follow-up of AEs and SAEs

After the initial AE/SAE report, the investigator is required to proactively follow each participant at subsequent visits/contacts. All SAEs, will be followed until resolution, stabilization, the event is otherwise explained, or the participant is lost to follow-up (as defined in Section 7.3). Further information on follow-up procedures is given in Section 10.3.

8.3.4 Regulatory Reporting Requirements for SAEs

Prompt notification by the investigator to the sponsor of an SAE is essential so that legal obligations and ethical responsibilities towards the safety of participants and the safety of a study intervention under clinical investigation are met.

The sponsor has a legal responsibility to notify both the local regulatory authority and other regulatory agencies about the safety of a study intervention under clinical investigation. The sponsor will comply with country-specific regulatory requirements relating to safety reporting to the regulatory authority, Institutional Review Boards (IRB)/Independent Ethics Committees (IEC), and investigators.

Investigator safety reports must be prepared for suspected unexpected serious adverse reactions (SUSAR) according to local regulatory requirements and sponsor policy and forwarded to investigators as necessary.

An investigator who receives an investigator safety report describing an SAE or other specific safety information (e.g., summary or listing of SAEs) from the sponsor will review and then file it along with the IB and will notify the IRB/IEC, if appropriate according to local requirements.

8.3.5 Pregnancy

Details of all pregnancies in female participants and, female partners of male participants will be collected after the start of study intervention and until last safety follow up (SFU) visit in the study.

If a pregnancy is reported, the investigator should inform the sponsor no later than 24 hours of learning of the pregnancy and should follow the procedures outlined in Section 10.4.

Abnormal pregnancy outcomes (e.g., spontaneous abortion, fetal death, stillbirth, congenital anomalies, ectopic pregnancy) are considered SAEs.

8.3.6 Liver-Related AEs

Investigators and participants should be alerted regarding non-specific symptoms which may be associated with liver dysfunction, including anorexia, nausea, fatigue, right upper abdominal discomfort, vomiting, malaise, jaundice, fever, and rash. Information on these symptoms should be asked for in case of abnormal liver laboratory values (see Table 7-1) or any other suspicion of liver dysfunction. The study participants should be reminded to contact the study site immediately, if they are concerned about such symptoms and unscheduled liver laboratory assessments should be considered.

A ‘close observation’ has to be initiated in case of ALT or AST >3ULN after start of study intervention (see Table 8-1) (26).

Abnormal laboratory results and clinical signs and symptoms resulting in close liver observation (CLO) should be promptly reported as adverse event if an overarching diagnosis is not yet available.

All events of ALT >3 × upper limit of normal (ULN) and bilirubin >2 × ULN or ALT >3 × ULN and international normalized ratio (INR) >1.5, if INR measured which may indicate severe liver injury (possible Hy’s Law), must be reported as an SAE.

Close observation includes:

- Repeat serum chemistry panel (including serum transaminases [AST and ALT] and serum bilirubin) 2 to 3 times per week. Frequency of retesting can decrease to once a week or less if laboratory abnormalities decrease and participant is asymptomatic.
- Obtaining a more detailed history of the symptoms and prior or concurrent diseases.
- Obtaining a history of concomitant drug use (including nonprescription medications and herbal and dietary supplement preparations), alcohol use, recreational drug use, and special diets.
- Ruling out acute viral hepatitis; autoimmune or alcoholic hepatitis; nonalcoholic steatohepatitis (NASH); hypoxic/ischemic hepatology and biliary tract disease. This may require performing additional procedures, e.g., ultrasound examinations. If requested, tests will be done retrospectively using residual blood/serum samples collected at visits before laboratory abnormalities occurred.
- Obtaining a history of exposure to environmental chemical agents.
- Obtaining additional tests to evaluate liver function as required, (e.g, international normalized ratio [INR], direct bilirubin measurements).

Stopping criteria for close observation:

- 2 consecutive normal/baseline results for liver enzymes in addition to availability of results from detailed CLO lab panel, related procedures, relevant medical and medication history and the reporting of signs and symptoms related to elevated liver enzymes, or
- a confirmed clinical diagnosis explaining the elevated liver enzymes.

Table 8–1: Close Observation Liver Safety Required Laboratory Assessments

Initial serum chemistry and coagulation panel	Albumin	First sample after AST or ALT > 3 X ULN
	Alkaline phosphatase	
	Alanine-aminotransferase (ALT / GPT)	
	Differential blood count	
	Cholinesterase	
	Conjugated (direct) bilirubin	
	Creatinine kinase	
	γ-GT (gamma-GT)	
	LDH	
	Total bilirubin	
	INR, aPTT	
Hepatitis serology	Anti-Hepatitis A virus IgM antibodies	
	- Hepatitis B virus surface antigen	
	- Anti-Hep. B surface antibodies	
	- Anti-Hep. B core total antibodies	
	- Anti Hep. B IgM antibodies	
	- Hepatitis B PCR (viral copies)	
	Anti-Hepatitis C virus antibodies	
	- Hepatitis C PCR (viral copies)	
	- Anti-Hepatitis D virus antibodies (if positive, automatically test HDV RNA)	
	- Anti-Hepatitis E virus IgM (if positive, automatically test HEV RNA)	
	Anti-Cytomegalovirus (CMV) IgM Antibodies	
	Anti-Epstein-Barr Virus (EBV) IgM Antibodies	
	Herpes simplex IgM (anti HSV IgM)	
Autoimmune serology	IgG level (gamma globulins)	
	Anti-mitochondrial antibodies	
	Anti-nat DNA Antibodies	
	Anti-sm Antibodies	
Metabolic and genetic etiology	A1AT level	
	Ceruloplasmin	
	Ferritin	
	Iron	
	Total iron binding capacity (TIBC)	
Follow-up samples during close observation:	Albumin	To be repeated 2 to 3 times per week until normalization of ALT or AST
	Alkaline phosphatase	
	Alanine-aminotransferase (ALT/ GPT)	

	Aspartate-aminotransferase (AST/ GOT)	
	Blood count, full (including eosinophils)	
	Cholinesterase	
	CK	
	Conjugated (direct) bilirubin	
	Total bilirubin	
	γ-GT (gamma-GT)	
	Hemoglobin	
	LDH	
Further laboratory tests to be considered*	Brucellosis, Leptospirosis (to be analysed from EDTA-blood sample), Toxoplasmosis	

*Additional further tests to be performed on case-by-case decision among Investigator, Medical Monitor and Lab Physician.

Abbreviations: A1AT = alpha-1 antitrypsin; ALT = alanine aminotransferase; aPTT = activated partial thromboplastin time; AST = aspartate aminotransferase; CK = creatine kinase; DNA = deoxyribonucleic acid; EDTA = ethylenediaminetetraacetic acid; GOT = glutamic oxaloacetic transaminase GPT = glutamic-pyruvic transaminase; GT = glutamyl transferase; HSV = Herpes simplex virus; IgG = immunoglobulin G; IgM = immunoglobulin M; INR = international normalized ratio; LDH = lactate dehydrogenase; PCR = polymerase chain reaction

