5.2 Exclusion Criteria

Participants are excluded from the study if any of the following criteria apply:

RUCC-related Medical Conditions

1. Smoking history within the last 12 months before screening (all forms of smoking, including e-cigarettes, cannabis and others), and any former smoker with more than 20 pack-years.
2. Ongoing or previous exposure to inhalational toxic fumes (e.g., ammonia, chlorine, nitrogen dioxide, phosgene and sulfur dioxide) within the last 12 months before screening.
3. Chest radiograph or CT within the last 24 months before screening and subsequent to the onset of chronic cough with presence of any obvious lung disease that could be responsible or contributing for the cough (e.g., bronchiectasis, cavitory lesions, interstitial pulmonary fibrosis, pneumothorax, pleural disease, unstable rib fracture, tuberculosis).

4. Forced expiratory volume in 1 second (FEV₁)/ Forced vital capacity (FVC) ratio < 60% or a history of frequent exacerbations of chronic obstructive pulmonary disease (COPD).
5. Respiratory tract infection within 4 weeks before screening.
6. History of chronic bronchitis.
7. Active state of massive hemoptysis⁵ or pulmonary hemorrhage, including those events managed by bronchial artery embolization or any history of bronchial artery embolization or massive hemoptysis within 3 months prior to screening.

Hepatic-related criteria

8. Moderate-to-severe hepatic impairment defined as Child-Pugh Class B or C.
9. ALT >2xULN, or AST >2xULN, or total bilirubin greater than ULN, or alkaline phosphatase (AP) >2x ULN, or INR greater than ULN (unless related to anticoagulation treatment).

Renal-related criteria

10. Estimated glomerular filtration rate (eGFR) <30 mL/min/1.73 m² calculated by Modification of Diet in Renal Disease (MDRD) formula.

Different eGFR formulas will be used for participants enrolled at sites in Japan in this study (for more details, see Section 10.6).

General Medical Conditions

11. Systolic blood pressure \geq 160 mmHg and/or diastolic blood pressure \geq 100 mmHg at screening visit.
12. Any other diseases or conditions that according to the investigator can compromise the function of the body systems and could result in altered absorption, excessive accumulation, impaired metabolism, or altered excretion of the study intervention (e.g., chronic bowel disease, Crohn's disease and ulcerative colitis).
13. Esophageal achalasia.

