6.5.1 Other Treatment Considerations

Apixaban, dabigatran, edoxaban, digoxin: prohibited within the last 2 weeks prior to screening visit and until 2 weeks after end of intervention period of this study.

Based on preclinical data, an increase in exposure of drugs that are sensitive substrates of OATP1B1/1B3, P-gp or BCRP during co-administration of BAY 1817080 due to inhibition of those transporters by BAY 1817080 cannot be excluded.

- Typical OATP1B1, OATP1B3, BCRP or P-gp substrates include but are not limited to the following: fexofenadine, sulfasalazine, rosuvastatin, atorvastatin, cerivastatin, glyburide, pravastatin, repaglinide, simvastatin.
- Participants receiving a combination of BAY 1817080 and OATP1B1/1B3, BCRP and P-gp substrates should be closely monitored for signs and symptoms of adverse events due to increased exposure of co-administered OATP1B1/1B3, BCRP or P-gp substrates. Dose modification of sensitive OATP1B1/1B3, BCRP or P-gp substrates should be considered based on the prescriber information or such compounds should be avoided.

A clinical DDI study investigating the effect of BAY 1817080 on the sensitive OATP1B1/1B3 and BCRP substrate rosuvastatin is ongoing.

According to the risk assessment based on the FDA Drug Development and Drug Interactions (DDI) guidance (18), the potential increase in exposure (AUC) due to inhibition of OATP1B1, the transporter with the lowest measured IC₅₀ is estimated to be up to 2.85-fold with the highest dose of 150 mg BID of BAY 1817080 (simulated steady state exposure of formulation B was used for DDI predictions). The parameters used for this calculation are

entirely based on IC₅₀ values determined in *in vitro* assays reflecting the maximum possible effect. The clinical relevant interaction will be assessed in the ongoing clinical DDI study investigating the effect of BAY 1817080 on the sensitive OATP1B1/1B3 and BCRP substrate rosuvastatin. Please refer to the current version of the IB for further information.

Additional information regarding other OATP1B1, OATP1B3, BCRP and P-p substrates can be found in Table 5-1 of the FDA DDI guidance (19).

Ketoconazole and other triazole antifungal drugs are allowed for topical/local use (including vaginal application) at any time during the study.

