7.1 Discontinuation of Study Intervention

It may be necessary for a participant to permanently discontinue study intervention. Such events are expected to be rare.

If study intervention is discontinued, a participant who is still in the intervention period should have the EoI visit (Visit 6) assessments performed as soon as possible. Following Visit 6, the participant continues to the follow-up period and the end of study visit (i.e., the SFU visit) assessments thereafter according to the SoA.

Participants *must* discontinue study intervention if any of the following occurs:

- In the investigator's opinion, continuation of the study intervention would be harmful to the participant's well-being
- Liver safety-related discontinuation criteria are met as described in [Table 7–1](#).
- Pregnancy (see Sections [8.3.5](#) and [10.4](#)).

Table 7–1: Liver Safety-Related Monitoring and Discontinuation Criteria

Lab result	Measures
ALT or AST >3 x ULN	
 • Repeat testing of ALT, AST and TBL 2-3 times a week • Withdraw study intervention if the participant cannot come for a repeat testing* • 'Close observation' as defined in Section 8.3.6
ALT or AST >3 x ULN and TBL >2 x ULN	Withdraw study intervention and initiate close observation as outlined in Section 8.3.6
ALT or AST >3 x ULN and INR >1.5 x ULN**	Withdraw study intervention and initiate close observation as outlined in Section 8.3.6
ALT or AST > 3 ULN with appearance of fatigue, nausea, vomiting, right upper abdominal quadrant pain or tenderness, fever, rash and/or eosinophilia (>5%)	Withdraw study intervention and initiate close observation as outlined in Section 8.3.6
ALT or AST >5 x ULN for more than 2 weeks	Withdraw study intervention and initiate close observation as outlined in Section 8.3.6
ALT or AST >8 x ULN	Withdraw study intervention and initiate close observation as outlined in Section 8.3.6

* i.e., in case no visit for a repeat testing could be arranged within a reasonable time frame despite efforts to contact the participant

** Relevant only if the participant is not on Vitamin K antagonist or heparin

Abbreviations: ALT = alanine aminotransferase; AST = aspartate aminotransferase; INR = international normalized ratio, TBL = total bilirubin, ULN = upper limit of normal (all referring to serum)

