10.2 Appendix 2: Clinical Laboratory Tests

The tests detailed in [Table 10–1](#) will be performed by the central laboratory, apart from urine pregnancy tests which are to be done at the trial sites.

Protocol-specific requirements for inclusion or exclusion of participants are detailed in [Section 5](#) of the protocol.

Additional tests may be performed at any time during the study as determined necessary by the investigator or required by local regulations.

Investigators must document their review of each laboratory safety report.

Laboratory/analyte results that could unblind the study will not be reported to investigative sites or other blinded personnel until the study has been unblinded.

Table 10–1: Protocol-Required Safety Laboratory Assessments

Laboratory assessments	Parameters
Hematology	Erythrocytes, Hemoglobin, Hematocrit, Leukocytes, Platelets
Blood Chemistry¹	Sodium, Potassium, Calcium, Magnesium, Phosphorus, Creatinine, Cystatin C, Total protein, Albumin, eGFR ²
Liver enzymes	Alkaline phosphatase, γ -GT (gamma GT), Alanine-aminotransferase (ALT, former GPT), Aspartate-aminotransferase (AST, former GOT), Total bilirubin
Carbohydrate metabolism	Serum glucose, Hemoglobin-A1C (HbA1C)
Lipids	Total cholesterol, Triglyceride, HDL-cholesterol, LDL-cholesterol
Coagulation	Prothrombin time (Quick), Activated partial thromboplastin time (aPTT), Fibrinogen, International normalized ratio (INR), Antithrombin III (ATIII) ³
Pancreas	Pancreatic α -amylase, Lipase
Pregnancy testing⁴	For women of child-bearing potential only, serum test at Visit 1, otherwise urine pregnancy tests every 4 weeks until the last study visit (SFU Visit)
COVID-19 testing⁵	Quantitative reverse transcription polymerase chain reaction (qRT-PCR) for SARS-CoV-2 nucleic acid, SARS-CoV-2 Immunoglobulin G antibodies

NOTES:

- 1 Details of liver chemistry stopping criteria and required actions and follow-up assessments after liver stopping or monitoring event are given in Section 8.3.6. All events of ALT $>3 \times$ upper limit of normal (ULN) and bilirubin $>2 \times$ ULN or ALT $>3 \times$ ULN and international normalized ratio (INR) >1.5 , if INR measured which may indicate severe liver injury (possible Hy's Law), must be reported as an SAE .
- 2 Estimated glomerular filtration rate calculated by Modification of Diet in Renal Disease (MDRD) formula. Japan-specific formula will be applied for participants enrolled at Japan sites (see Section 10.6).

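### The mandatory liver SAE rule names ALT only, although the withdrawal rule and the SAP count use ALT or AST

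*Protocol*

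**What the plan says.** Protocol 8.3.6 defines two patterns that have to be reported as SAEs. The sentence opens "All events of ALT >3 × upper limit of normal (ULN) and bilirubin >2 × ULN or ALT >3 × ULN", and its second limb continues with "international normalized ratio (INR) >1.5, if INR measured which may indicate severe liver injury". Note 1 to Table 10-1 (Protocol 10.2) repeats the rule, including the clause "if INR measured which may indicate severe liver injury". Neither place mentions AST.

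Three other liver rules use both enzymes:

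- **Close observation (Protocol 8.3.6).** The trigger is ALT or AST above 3 x ULN.
- **Withdrawal (Protocol 7.1, Table 7-1).** The combined rows are "ALT or AST >3 x ULN and TBL >2 x ULN" and "ALT or AST >3 x ULN and INR >1.5 x ULN"; each requires study drug to be withdrawn. A footnote limits the INR row: "Relevant only if the participant is not on Vitamin K antagonist or heparin".
- **Combined count (SAP 6.4.3).** Participants are counted if ALT or AST exceeds 3 x ULN together with bilirubin above 2 x ULN or INR above 1.5 x ULN. SAP 6.4.3.1 sets the INR range at 2.0 to 3.0 for vitamin K antagonist (VKA) users and 0.8 to 1.2 for everyone else.

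Protocol 8.3.1 requires SAEs to reach the sponsor within 24 hours. Protocol 10.3.2 lets the investigator classify other important medical events as serious by judgment.

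**The concern.** The same combined abnormality is treated differently according to which transaminase is raised. If it is ALT, the 24-hour report is automatic. If it is AST alone, the participant must come off drug and will appear in the SAP count, but the expedited report depends on the site's judgment. Two sites could classify identical laboratory results differently.

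Liver function change is a named potential risk (Protocol 2.3.3.4, citing bile salt export pump inhibition in one of two in vitro assays). The synopsis states that there is no data monitoring committee, so SAE reporting is a main expedited route for a liver signal. Neither document gives a reason for the narrower reporting rule. The Amendment 1 history in Protocol 10.8.1 says the liver AE and SAE reporting criteria were changed to remove inconsistency, which makes a deliberate ALT-only choice less likely, though it does not rule one out.

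**Working it through.** The plan states no figure to reproduce. The check applies each rule as written to the same cases.

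**Rules** (ALT, AST and bilirubin in multiples of ULN):

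- SAE rule now (8.3.6; Table 10-1 note 1): ALT > 3 and (bilirubin > 2 or INR > 1.5).
- Table 7-1, combined rows: (ALT or AST > 3) and (bilirubin > 2, or INR > 1.5 x ULN if not on a VKA or heparin).
- SAP 6.4.3 count: (ALT or AST > 3) and (bilirubin > 2 or INR > 1.5 x ULN), with values from the same sample (bilirubin) or same date (INR).
- SAE rule with AST added: (ALT or AST > 3) and (bilirubin > 2 or INR > 1.5).

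**INR cut-offs.** From SAP 6.4.3.1: 1.5 x 1.2 = 1.8 for participants not on a VKA, and 1.5 x 3.0 = 4.5 for VKA users. The protocol gives no INR ULN for Table 7-1. Assuming 1.0 to 1.3, the cut-off lies between 1.5 x 1.0 = 1.5 and 1.5 x 1.3 = 1.95. An INR of 2.0 exceeds it throughout, so the results below do not depend on that assumption.

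**Results.** 'AST only' means AST > 3 with ALT not > 3.

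| Case | SAE rule now | Table 7-1 combined rows | SAP count | SAE rule with AST |
|---|---|---|---|---|
| 1. ALT > 3, bilirubin > 2 | yes | yes | yes | yes |
| 2. AST only, bilirubin > 2 | **no** | yes | yes | yes |
| 3. ALT > 3, INR 2.0, no anticoagulant | yes | yes | yes | yes |
| 4. AST only, INR 2.0, no anticoagulant | **no** | yes | yes | yes |
| 5. ALT > 3, INR 2.5 on a VKA | yes | no | no | yes |
| 6. AST only, INR 2.5 on a VKA | no | no | no | yes |

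Cases 2 and 4 are the gap: withdrawal is required and the SAP counts the participant, but no automatic SAE follows. Adding AST closes both. Case 5 is unaffected by the change. Case 6 is a side effect of it, taken up under the fix.

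**The case against.** The strongest reply is that these rules do different jobs. Table 7-1 decides when to stop drug, SAP 6.4.3 decides what to tabulate, and 8.3.6 decides what is reported urgently as possible Hy's Law. Different triggers need not contradict one another, and the SAP's eDISH plot is also ALT by bilirubin. This stands as far as it goes: an ALT-only rule could be chosen on purpose. But neither document says so, and the close-observation trigger in the same section names both enzymes.

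The second reply is that AST-driven cases are well covered, and this also stands. They stop drug, enter close observation and are promptly reported as AEs; AEs leading to discontinuation are followed up and listed; central laboratory data reach the sponsor electronically; the SAP lists everyone with ALT or AST above 3 x ULN; and the investigator may still call the case serious. A reader might infer that such cases go unseen. The documents do not support that: what is missing is only the automatic trigger.

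A reader might also infer that a therapeutic INR in a VKA user is in itself an automatic SAE. VKA users can enrol: exclusion criterion 9 reads "INR greater than ULN (unless related to anticoagulation treatment", and the list in 6.5.1 ("Apixaban, dabigatran, edoxaban, digoxin: prohibited within the last 2 weeks prior to screening visit") names no VKA. But the SAE rule also requires ALT above 3 x ULN. What remains is case 5, an extra report on someone already under close observation, which errs towards caution. The absolute INR limit of 1.5 for participants not on anticoagulants can be read in the same way.

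**Conclusion.** The point holds for AST. Both statements of the compulsory SAE rule omit an enzyme that the withdrawal rule, the close-observation trigger and the SAP count include, so some cases that force withdrawal are not automatically reported within 24 hours.

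Its size is modest. It concerns SAE classification and the speed of reporting only. The SAP's bilirubin and INR counts are taken from laboratory values, so a reader who infers that those counts are wrong, or would change with the SAE rule, would be mistaken. Efficacy is unaffected. The documents give no rate for AST-predominant cases and report no drug-related change in liver parameters to date, so no frequency is claimed.

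The conclusion rests on reading the SAE sentence as exhaustive for automatic reporting, with 10.3.2 as the only other route to SAE status for a case that meets no other seriousness criterion.

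**What to change.** In Protocol 8.3.6 and in note 1 to Table 10-1, write 'ALT or AST >3 x ULN' in both limbs of the sentence. Table 7-1 and the SAP stay as they are. If ALT-only is intended, a sentence of rationale in 8.3.6 should say so.

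No new data are needed: ALT, AST, bilirubin and INR are already in the central laboratory panel. The cost is a few more SAE reports and a small protocol amendment, to be communicated to sites in the 19 countries named in 6.3 (Japan 1, Europe 11, rest of world 7), with ethics approval if it is classed as substantial.

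One side effect should be accepted knowingly. Because the INR limb makes no allowance for anticoagulants, adding AST extends automatic reporting to VKA users at target INR with AST above 3 x ULN (case 6), as already happens for ALT (case 5). This is cautious over-reporting. Whether and how to relax it is the sponsor's choice and not part of this fix. Borrowing the SAP's VKA range for the purpose would turn a tabulation limit into a less sensitive reporting rule for sites.
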